7.5.4. Acceptability of Fresh Start amongst HCPs

Interviews are to be carried out by members of the research team from the Institute of Global Health Innovation (IGHI) at Imperial College London and will form part of a qualitative analysis. Interviews conducted with HCPs will be analysed using NVivo, where responses will undergo thematic analysis using an inductive approach to derive key themes.

7.5.5. Cost-effectiveness of delivering Fresh Start

From the three sets of data established in 6.2.6, cost-effectiveness of Fresh Start is to be assessed via the following:

- Number of primary care appointments per patient - as entered in study dataset over the 12-week assessment period

Summary statistics will be derived for mean, sd, median, 1st/3rd quartiles, and minimum/maximum. Results will be presented as mean (SD) for normally distributed data and median [Q1-Q3] for skewed.

To assess for differences in frequency of appointments per patient between Fresh Start and the matched control group, a Poisson-based mixed effects model with covariates for sex, age, social deprivation index will be used allowing for clustering by GP practice.

- Cost per appointment per patient - as entered in study dataset

Summary statistics will be derived for mean, sd, median, 1st/3rd quartiles, and minimum/maximum. Results will be presented as mean (SD) for normally distributed data and median [Q1-Q3] for skewed.

To assess for differences in cost of appointments per patient between Fresh Start and the matched control group, a mixed-model approach with covariates for sex, age, social deprivation index will be used allowing for clustering by GP practice.

- Cost of equipment per patient

Imperial Clinical Trials Unit	SUB-STUDY SAP TEMPLATE – SUB-ANALYSES AND OBSERVATIONAL STUDIES	SOP_TEM_BS002
-------------------------------	---	---------------

Costs per patient will be estimated using the figures provided in section 6.2.6.1. Once established, summary statistics will be derived for mean, sd, median, 1st/3rd quartiles, and minimum/maximum. Results will be presented as mean (SD) for normally distributed data and median [Q1-Q3] for skewed

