7.1. General Methodology

7.1.1. Descriptive Output for Feasibility Outcomes

To investigate feasibility of Fresh-Start, analysis of primary endpoints will be descriptive in nature to establish how many patients engaged with the Fresh Start program, and if so, to what extent.

Continuous variables will be presented as means and standard deviations if normally distributed, and as medians and inter-quartile ranges for skewed data. Categorical variables will be presented as frequencies and percentages.

Details of the output provided will be included within sections 7.5.1 – 7.5.5. Dummy shells for tables, figures and listings will be provided within appendix 2.

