7.1.2. Propensity Score Matching

For the primary cost-benefit comparison and secondary safety and efficacy comparisons, study data will be compared against a matched-control group established via propensity score matching. This is achieved by deriving a propensity score for each enrolled patient based on the following characteristics:

- Age
- Gender
- Geographical proximity
- Social deprivation index (by practice)

- Ethnicity

Using the above categories, taking 'arm' as the dependent variable, logistic regression using a generalised logit model will be used to generate the estimated propensity scores. Scores are also applied to a control 'arm' taken from the WSIC database as section 5.2.2 with everyone in the matched control identified within one month of the index case. The scores are then used to 'pair-up' patients within both groups, patients will be matched on a 1:1 basis without replacement.

Scores are to be calculated using PSOCORE in STATA. Matching is to be carried out using PSMATCH2 (or a suitable alternative). Balancing on matching variables is to be checked once matching is completed using PSTEST. If any variable is found to be unbalanced the matching is repeated, either adjusting the matching method or caliper used.

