7.2. Summary of Analysis Methods

Primary Objective	Outcome	Comp. w/ control?	Analysis Methods
1) To assess the feasibility of uptake amongst people with 'high risk' or 'very high risk' type 2 diabetes .	offered Fresh Start vs. enrolled	No	Frequency and percentage enrolled presented
	enrolled vs. downloading app	No	Frequency and percentage downloading presented
2) To assess the usability of Fresh Start amongst people with 'high risk' or 'very high risk' type 2 diabetes .	VGCs attended	No	Summary stats of VGCs attended overall and per unit time
	emails metrics as section 7.5.2	No	Frequency and percentages presented
	blood glucose measurements recorded	No	Summary stats of meas. recorded by patient overall and per unit time
	blood pressure measurements recorded	No	Summary stats of meas. recorded by patient overall and per unit time
	weight* measurements recorded	No	Summary stats of meas. recorded by patient overall and per unit time
	Diabetes Distress Scale measurements recorded	No	Summary stats of meas. recorded by patient overall and per unit time
4) To assess the acceptability of Fresh Start amongst people with 'high risk' or 'very high risk' type 2 diabetes .	Interviews with patients (x10)	No	As per ICHP team
5) To assess the acceptability of Fresh Start amongst HCPs .	Interviews with healthcare professionals (HCPs, x10)	No	As per ICHP team
6) To assess the cost-effectiveness of delivering Fresh Start.	primary care appointments per patient (as recorded)	Yes	Summary stats of no appts. attended per patient up to 6 months post enrollment

Primary Objective	Outcome	Comp. w/ control?	Analysis Methods
			Comparison between groups via poisson mixed model
	Cost per appointment per patient	Yes	Summary stats of appt. cost per patient. Comparison between groups via mixed model
	Cost of equipment per patient	No	Summary stats of overall cost per patient.

Secondary Objective	Outcome	Comp. w/ control?	Analysis Methods
1) To assess the safety of Fresh Start.	Number of deaths	Yes	Frequency and percentages presented up to 6 months post enrollment
	Number of emergency department admissions	Yes	Frequency and percentages presented up to 6 months post enrollment
	Number of hospital admissions	Yes	Frequency and percentages presented up to 6 months post enrollment. Difference presented with 95% CI
2) To assess the impact of Fresh Start on clinical outcomes .	HbA1c	Yes	Summary stats of HbA1c by visit (BL, W12, M6) Comparison within & between groups via mixed model

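### Primary care appointments, a primary cost outcome compared with control, are counted over 12 weeks in SAP 6.2.5 and 7.5.5 but up to 6 months in SAP 7.2; appointment cost is loosely defined and never combined with equipment cost in a comparison with control

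*SAP*

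**What the plan says.** Cost-effectiveness is a primary objective in both documents, and SAP 5.2.2 lists it among those needing the matched control group.

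**Window.** SAP 6.2.5 and 7.5.5 use the same definition: "Number of primary care appointments per patient - as entered in study dataset over the 12-week assessment period". In 7.5.5 a Poisson mixed model against control follows that definition. The SAP 7.2 row for the same outcome reads "Summary stats of no appts. attended per patient up to 6 months post enrollment", followed by a Poisson mixed-model comparison with no window of its own. Protocol 3.6 gives no window; it says only that the data come from the EPR. SAP 7.1.1 states "Details of the output provided will be included within sections 7.5.1" and onwards to 7.5.5. For controls, SAP 7.1.2 says only "with everyone in the matched control identified within one month of the index case".

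**Appointment cost.** SAP 7.5.5 names the item "Cost per appointment per patient - as entered in study dataset" but introduces its model with "To assess for differences in cost of appointments per patient between Fresh Start and the matched control group". No formula or window is given.

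**Equipment and total.** SAP 7.1.2 says "For the primary cost-benefit comparison and secondary safety and efficacy comparisons, study data will be compared against a matched-control group". Equipment cost is marked as not compared with control in Protocol 3.6 and in SAP 6.1 and 7.2. The phrase "Summary stats of overall cost per patient" in SAP 7.2 belongs to the equipment row, and SAP 7.5.5 builds that figure from equipment prices alone. SAP Appendix 1 lists costing outputs for appointments (5.1.1-2), appointment cost (5.2.1-2) and equipment (5.3), and none for a total.

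**The concern.** Two analysts following the SAP could count the same primary outcome over periods that differ about twofold (26/12 = 2.17, taking 6 months as 26 weeks). That would be only a matter of precision if contacts accrued evenly. They do not: Fresh Start's own contacts are concentrated in the first 12 weeks, so lengthening the window dilutes them with ordinary appointments.

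The cost item has a similar problem. A group session may cost less per attendee than an ordinary appointment. Adding such sessions would lower the mean cost per appointment while raising the sum per patient, so the two readings can point in opposite directions.

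Finally, equipment is a cost that only Fresh Start patients incur. If it stays outside the comparison, the result set against control omits part of what the service costs.

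**Working it through.** **1. The passages side by side.** The definition (SAP 6.2.5) and the detailed method (SAP 7.5.5) say 12 weeks; the summary table (SAP 7.2) says 6 months. All are current text. They might be read as a 12-week comparison plus a 6-month description, but SAP 7.5.5 already plans summary statistics under its 12-week definition, and Appendix 1 provides one appointments entry using one descriptive template and one model template. Where the SAP wants both horizons, as for HbA1c, lipids and weight in 7.6.2, it says so.

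**2. Where contacts fall.** Protocol 3.7 puts the first VGC about one week after onboarding and the others at four-week intervals, so roughly weeks 1, 5 and 9. The review in SAP 5.2.1 comes at the end of the 12 weeks, on the boundary. A possible repeat cycle (SAP 5.2.1) and the month-6 visit (Protocol 3.9) come later. The SAP does not say which of these count as primary care appointments.

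**3. Illustration of the window.** The documents give no appointment rate. Assume b ordinary appointments per 12 weeks in both groups, k service contacts per participant, full attendance and no repeat cycle.

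- 12-week ratio = (b + k)/b
- 26-week ratio = (26b/12 + k)/(26b/12); add 1 to the numerator if the month-6 visit counts

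k = 5 is onboarding, three VGCs and the review; k = 3 is the VGCs alone.

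| b | k=5, 12 wk | k=5, 26 wk | k=5, 26 wk with month-6 visit | k=3, 12 wk | k=3, 26 wk |
|---|---|---|---|---|---|
| 1 | 6.00 | 3.31 | 3.77 | 4.00 | 2.38 |
| 2 | 3.50 | 2.15 | 2.38 | 2.50 | 1.69 |
| 4 | 2.25 | 1.58 | 1.69 | 1.75 | 1.35 |

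If the review falls just outside 12 weeks (k = 4), the 12-week ratios are 5.0, 3.0 and 2.0. With k = 0 the ratio is 1.0 in both windows, unless the month-6 visit is counted.

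**4. Unit cost against sum.** Take b ordinary appointments at cost 1, unchanged by the service, plus three VGCs at cost v per attendee. The mean per appointment is (b + 3v)/(b + 3), below the control value of 1 for any v < 1. The sum relative to control is (b + 3v)/b, above 1 for any v > 0. With b = 2 and v = 0.25, 0.50, 0.75 (assumed), the mean is 0.55, 0.70, 0.85 and the sum is 1.38, 1.75, 2.13 times control.

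**5. Equipment (SAP 6.2.6).** One each of glucometer, strips, lancets, sharps bin and scale: 2.00 + 5.95 + 3.77 + 3.00 + 20.00 = 34.72. With the M4 monitor, 34.72 + 37.93 = 72.65; with the HEM-9210, 34.72 + 130.00 = 164.72. No currency, pack size or quantity is stated, so one unit of each consumable is an assumption.

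**The case against.** - **Two rival control comparisons.** A reader might infer that the SAP specifies two comparisons with different windows. It does not clearly do so. In SAP 7.2 the 6-month phrase belongs to the summary statistics; the only comparison placed under a stated window is the 12-week one in 7.5.5, and 7.1.1 favours that section. This stands, and makes 12 weeks the natural choice. It does not remove the unreconciled text or supply a start date for controls.

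- **The plan cannot say whether Fresh Start costs more.** This is too strong. The 7.5.5 model wording and the 7.2 row both lean towards a per-patient sum. Controls receive no equipment, so under that reading the mean total difference is the appointment-cost difference plus mean equipment cost, and both are planned outputs. Equipment cost would also be visible beside any appointment saving. What is missing is a joint comparison with a confidence interval.

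- **The protocol chose separate components.** Protocol 3.6 lists three outcomes and marks equipment as not compared with control. That is a fair reason to treat the total as an addition rather than the repair of a broken analysis.

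- **The illustrated ratios measure the error.** They do not. They need full attendance, although VGC attendance is itself an outcome, and k = 5 counts onboarding, which Protocol 3.7 lets administrative staff deliver. Nor is the opposite-direction cost result inevitable: with b = 2 and v = 0.25, a fall of more than 3 × 0.25 = 0.75 ordinary appointments makes the sum favour Fresh Start too.

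**Conclusion.** The inconsistency in the window is certain, and it concerns a primary outcome compared with control. It should be corrected, although the text already leans towards 12 weeks. Its effect on the estimate depends on whether service contacts count as appointments: there is none if no such contact counts in either window, and it can be substantial if they do. The actual size cannot be computed from the documents, so the tabulated ratios show only direction and sensitivity.

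The appointment-cost wording needs clarifying; a per-patient sum is the likelier intention. The absence of a joint total is a gap against the comparison announced in SAP 7.1.2, but a limited one, since the mean can be assembled from separate tables under the sum reading. The kit figures indicate scale: an appointment saving smaller than the kit cost would sit alongside a higher combined cost, with no interval for the combined figure.

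None of this affects enrolment or data collection.

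**What to change.** Amend the SAP before between-group results are seen:

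1. Change SAP 7.2 to 12 weeks for the appointment comparison, matching 6.2.5 and 7.5.5. Keep 6 months as a labelled secondary summary, shown with and without the month-6 visit.
2. Start counting at one defined date for participants, for example the recorded enrolment date; SAP 6.2.1 defines enrolment as entry in the dataset but gives no date. Give each control the matched participant's date. Use the same window length in both groups, with no extension for Fresh Start only.
3. State which service contacts (onboarding, VGCs, 12-week review) count as appointments, and show the count with and without them.
4. Define appointment cost as the sum over the patient's appointments in that window. Add equipment cost, zero for controls, and report the between-group difference in the total with a 95% CI. Record this as an added SAP summary, because Protocol 3.6 marks equipment as not compared with control.

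Minor: SAP 6.3.1 uses 12 weeks for the exploratory safety outcomes, whereas 7.2 and 7.6.1 use 6 months; align 6.3.1 with the other two.

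The cost is SAP wording and a little extra analysis, using cost data the plan already calls for. The downside is that Fresh Start's cost may look less favourable.

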Huma will also provide a “Clinician Dashboard” to review patient reported data to inform care decisions. The Huma Clinician Dashboard will be used to monitor the blood pressure and blood glucose measurements of participants as they are entered into the Huma app. A HCA at each practice will review the Huma clinician dashboard and escalate any urgent readings to the GP. Data from the dashboard will be provided to PNs in advance of VGCs and will be used to trigger non-urgent care protocols before and after VGC sessions.

[figure not shown]
Staff actions at primary care practice:

- Review Huma Clinician Dashboard daily
- Escalate to GPs when there has been an urgent reading

Patient iPhone and Android app

Clinician Dashboard

Patient Remote Monitoring Devices

- Blood pressure cuff
- Blood glucometer, strips and lances
- Digital scales

Video group consultations (VGCs)

VGCs will be booked and the process for VGCs explained during onboarding. Participants will be booked onto their first VGC approximately one week from the date of the onboarding session, with the second and third booked at four week intervals. Reminder emails containing the Microsoft Teams link to join the session will also be set up during this session. Each VGC will last for 1 hour and 15 minutes in total.

Staff actions at primary care practice **before each VGC**:

- Open Huma Clinician Dashboard patient template side-by-side and manually port patient-reported data from the Huma app into the EPR as follows for patients due to attend VGC session
 - 1 x latest blood pressure reading
 - 1 x latest blood glucose

Imperial College London

[figure not shown]
- 1 x latest Diabetes Distress Score
- 1 x latest weight (BMI automatically calculated)
- Average daily step count for the last week (total for the week / 7)
- Open VGC Discussion Board slide and populate using EPR data
 - Blood pressure – latest reading
 - Blood glucose – latest reading
 - DDS – latest reading
 - BMI – latest reading
 - Average daily step count for the last week (total for the week / 7)
- Review food pictures in Huma dashboard
 - Decide whether to discuss food pictures for that patient on VGC session

Staff actions at primary care practice **during each VGC**:

- Set-up Teams meeting and troubleshoot potential problems with participants (15mins before session start time)
- Take consent
- Share link for Fresh Start emails
- Introductions and theme (video played – 10/15 slides talked to)
- Answer questions in the chat

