5.1. Study Design

An experimental feasibility study with an additional exploratory pre-test/post-test design using a matched control implemented via propensity score matching.

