6.2.5. Cost-effectiveness of delivering Fresh Start

Cost-effectiveness is to be determined by the following measures:

- Number of primary care appointments per patient - as entered in study dataset over the 12-week assessment period
- Cost per appointment per patient - as entered in study dataset
- Cost of equipment per patient – defined below:

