7.6. Secondary Analysis Methodology

7.6.1. Safety of Fresh Start

From the safety parameters established in 6.3.1, safety of Fresh Start is to be assessed via the following over 6 months:

- Number of deaths

Number of deaths is to be presented by frequency per group.

- Number of emergency department admissions

Number of patients with emergency admissions is to be presented by frequency per group

- Number of hospital admissions

Frequency of events per patient is to be presented in a frequency table by treatment group with percentages to 1 dp.

Number of patients with hospital admissions is to be presented by frequency per group

Statistical comparison of safety will consist of a composite outcome, including all three events listed above. Number of patients with a safety event occurring is to be presented by frequency per group with difference in number of patients presented with a 95% CI.

7.6.2. Impact of Fresh Start on clinical outcomes.

From the clinical outcome parameters established in 6.3.2, potential efficacy of Fresh Start is to be assessed via the following

- **HbA1c, at baseline, 12-week and at 6 months**
- **Lipids, at baseline, 12-week and at 6 months**
- **Weight, at baseline, 12-week and at 6 months**

Tables displaying summary statistics will be produced displaying mean, SD, median, minimum & maximum at timepoints BL, W12 & M6

Within-group change from baseline at 12 weeks will be assessed via a mixed-effects model taking values at 12-weeks as the dependant variable and adjusting for covariates; baseline, sex, age, social deprivation index and allowing for clustering by GP Practice

Between-group differences in change from baseline at 12 weeks will be analysed using a similar mixed-effects model including an additional parameter for treatment effect and again adjusting for covariates; baseline, sex, age, social deprivation index and allowing for clustering by GP Practice

Further analysis will take place once long-term (6-month) follow-up is completed using an adjusted version of the above models containing additional terms for visit and visit*treatment interaction.

- **Diabetes Distress Scale score (DDS), as recorded within HUMA once monthly across the 12-week assessment period and also at 6 months**

Summary statistics displaying mean, SD, median, minimum & maximum DDS will be produced at for first reading and last reading.

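### The primary appointment comparison does not say whether Fresh Start's own contacts count and uses no pre-index count, so its rate ratio cannot be read as replacement of usual care

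*SAP*

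**What the plan says.** Cost-effectiveness is a primary objective in both documents. Its appointment count and appointment cost are the only primary outcomes that SAP 6.1 marks for comparison with control.

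- **Outcome.** SAP 6.2.5 defines it as "Number of primary care appointments per patient - as entered in study dataset over the 12-week assessment period", and 7.5.5 repeats this. The summary table in SAP 7.2 has a different window: "Summary stats of no appts. attended per patient up to 6 months post enrollment".
- **Model.** To test for "differences in frequency of appointments per patient between Fresh Start and the matched control group", SAP 7.5.5 specifies "a Poisson-based mixed effects model with covariates for sex, age, social deprivation index will be used allowing for clustering by GP practice". The appointment cost model has the same covariates.
- **Matching.** SAP 7.1.2 builds the propensity score from age, gender, geographical proximity, deprivation and ethnicity, and then "patients will be matched on a 1:1 basis without replacement". Prior use of primary care is not on the list.
- **Contrast.** For HbA1c, lipids and weight, SAP 7.6.2 does use the starting value: "adjusting for covariates; baseline, sex, age, social deprivation index and allowing for clustering by GP Practice".
- **Service contacts.** Protocol 3.4 and 3.7 describe an onboarding appointment, three VGCs and a one-to-one review at the end of the 12 weeks. On timing, Protocol 3.7 says "Participants will be booked onto their first VGC approximately one week from the date of the onboarding session", with the other two at four-week intervals. Controls are untreated and have none of these.

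Neither document says whether these contacts are appointments for the purpose of the count. VGC attendance is itself listed as an EPR-sourced outcome.

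**The concern.** The rationale in Protocol 1.2 is equal or better care without higher expenditure, and possible savings in time and cost. Two different quantities bear on that: how many contacts a Fresh Start patient uses in total, and whether the service's contacts displace other primary care. A single undivided ratio addresses at most the first, and only if the reader knows what was counted.

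Because the rule is missing, two analysts could follow the SAP faithfully and report ratios on opposite sides of 1 from the same patients. Practices may also code differently: onboarding may be done by a nurse, a healthcare assistant or administrative staff, remotely or face to face.

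The second gap is confounding. Patients choose to enrol. If those who do already attend more or less often than their matched controls, that difference enters the estimate as if the service had caused it, and nothing in the model or matching addresses it.

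**Working it through.** The plan gives no expected appointment rate, effect size or power for this comparison, so there is no stated figure to reproduce. The check asks how far the ratio depends on the missing rule.

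**Inputs**
- C, service contacts in 12 weeks: onboarding 1 + VGCs 3 + review 1 = 5 (Protocol 3.4, 3.7). This assumes full attendance.
- L, control appointments in 12 weeks: not in the documents; assumed 2 to 8.
- r, share of usual care replaced: 0, 0.5 or 1.

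**Formula**
If service contacts count: ratio = (C + L(1 − r)) / L = (1 − r) + C/L.
If they do not: ratio = 1 − r.

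| L | r = 0 | r = 0.5 | r = 1 |
|---|---|---|---|
| 2 | 3.5 | 3.0 | 2.5 |
| 4 | 2.25 | 1.75 | 1.25 |
| 5 | 2.0 | 1.5 | 1.0 |
| 6 | 1.83 | 1.33 | 0.83 |
| 8 | 1.625 | 1.125 | 0.625 |
| any L, contacts not counted | 1.0 | 0.5 | 0 |

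Going from no replacement to full replacement lowers the ratio by 1. The counting rule shifts it by C/L, which is 2.5 at L = 2 and 0.625 at L = 8.

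**Break-even under full replacement.** The ratio exceeds 1 only if L < C. That is fewer than 5 control appointments in 12 weeks (5/12 × 52 = 21.7 a year). If only the three VGCs are coded or attended, it is fewer than 3 in 12 weeks (13 a year). In the 6-month window, adding the month-6 appointment of Protocol 3.9 gives C = 6, so fewer than 6 in 26 weeks (12 a year), before any repeat of the service.

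**Does a pre-index count repair this?** A Poisson simulation used 300 patients per arm, C = 5, L = 2 and overdispersed usual care, without practice clustering or the other covariates:
- All contacts, no pre-index count: 3.49, 3.02 and 2.52 for r = 0, 0.5 and 1.
- All contacts, with pre-index count: 3.49, 3.02 and 2.51.
- Non-programme contacts only, with pre-index count: 1.00, 0.50 and 0.

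The separation recovers replacement; the pre-index count does not.

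**What the pre-index count does address.** With prior use assumed 1.3 times higher in Fresh Start and r = 0, the all-contact ratio is 3.84 unadjusted and 3.62 adjusted, against 3.5 with no imbalance. For non-programme contacts the unadjusted value is 1.3 by construction, the adjusted value is 1.15, and the truth is 1.0. One noisy count removes about half of the bias in this case.

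**The case against.** The strongest reply is that the objective concerns the cost-effectiveness of delivering the service. Contacts the service creates are real resource use, so counting them is correct, and replacement of usual care is a further question. That stands: the total should stay. It does not excuse leaving the count undefined, and a total alone cannot say whether anything was saved elsewhere.

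It can also be said that SAP 7.5.2 already summarises VGCs attended per patient, so part of the breakdown exists. That is true, but it covers VGCs alone and does not enter the comparison with control.

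A reader might infer more than the documents support:
- *That the plan pools the contacts.* It neither includes nor excludes them; it is silent.
- *That Fresh Start must show more appointments even if it replaced all usual care.* This needs a control mean below the number of programme contacts counted, and that mean is not given. Patients are invited to the VGCs and the review, so fewer than five may be attended.
- *That the missing pre-index count produces the excess.* The simulation shows it does not; it is a separate problem.
- *That the month-6 visit is a research visit charged to the service.* Protocol 3.9 does not call it that, and it lies outside the 12-week window.
- *That the pre-test/post-test label commits the plan to a prior count.* SAP 5.1 describes an "additional exploratory pre-test/post-test design using a matched control", and Protocol 3.11 ties pre/post change to clinical outcomes.
- *That VGCs will be costed as one-to-one visits.* No costing rule is given either way.

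**Conclusion.** The concern holds as a gap in definition and in adjustment. The SAP does not state which contacts are appointments. At an assumed 2 control appointments per 12 weeks with full attendance, that omission alone moves the ratio by 2.5, more than the 1.0 that separates no replacement from full replacement. If programme contacts are counted, the single ratio cannot show replacement of usual care. Its direction under full replacement depends on a control rate the documents do not give: 2.5 at 2 appointments, 1.0 at 5 and 0.83 at 6.

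The absence of any pre-index count is a distinct weakness in a non-randomised comparison where 300 of 1,500 identified patients (20%) are expected to enrol. Its size is unknown; the 1.3-fold imbalance is illustrative.

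The 12-week and 6-month windows in the SAP conflict, and the choice changes which service contacts can enter. These points should be settled before analysis. They do not invalidate the total as a measure of service use.

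**What to change.** 1. In SAP 6.2.5 and 7.5.5, state which contacts count. Keep total appointments as the service-use comparison. Also report and model contacts excluding VGCs and onboarding. Leave routine reviews and blood-test visits in for both arms, because removing them from Fresh Start alone would bias the comparison in its favour. The retained 12-week review has a price: at L = 2 and full attendance, the split ratio is (2(1 − r) + 1)/2 = 1.5, 1.0 or 0.5 for r = 0, 0.5 or 1 if the review is additional to usual care. The number of such reviews should be shown beside it.
2. Extract a same-length pre-index appointment count from the EPR/WSIC for both arms. Add it to the Poisson and cost models, and preferably to the propensity score.
3. Cost each VGC as session cost divided by the number attending. With 6 to 10 patients per session, charging the whole session to every attendee would overstate its cost 6- to 10-fold.
4. Reconcile the 12-week window in SAP 6.2.5 and 7.5.5 with the 6-month window in SAP 7.2. The longer one adds the month-6 appointment and any repeat of the service.

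The cost is SAP wording, one look-back field and one flag per contact. The flag depends on VGC and onboarding contacts being identifiable in the EPR; VGC attendance is already sourced there, but onboarding may be harder to find.
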